**E. Study Design**

**1. Overview of Study Design.** When a patient is at elevated risk of suicide, the PCC will be prompted by Opioid Wizard to complete the CSSRS, easily available to all PCCs in the EHR and saved as discrete data elements. Risk-based (depending on CSSRS score) referral and follow-up recommendations for suicide prevention will be given, with specific care recommendations ranging from care as usual (very low risk) to referral to behavioral health for evaluation and safety planning (moderate to high risk) to immediate evaluation in the emergency department and potential inpatient admission (very high risk), building on workflows developed for use by care managers in our recently completed suicide prevention trial of over 19,000 people at elevated risk of suicide.

The MHRN suicide risk models will be programmed into the EHR, a rigorous process that will take approximately 6 months. This process includes building the model in a testing environment in the EHR, testing the model with fictitious patients in a EHR testing environment and conducting chart audits, revising as needed, testing the model in a different EHR testing environment with real patient data, revising as needed, testing the model by running it silently in the EHR production environment and conducting chart audits, and revising as needed. This is followed by testing in the EHR production environment with 5-15 physicians in 1-2 pilot clinics. Prior to the go-live date for the suicide risk calculator, training on use and interpretation of the suicide risk model and the CSSRS will be provided to all PCCs and their rooming staff in intervention clinics. Training for control clinics will be separate and will provide training on the use of the CSSRS.

**2. Duration of Study and Visit Schedule.** In the parent trial, HealthPartners primary care clinics (n=30) will be randomized to receive or not receive access to the OUD-CDS. In this supplemental study, the clinics receiving access to the OUD-CDS (n=15) will be further randomized (1:1) to receive or not receive access to the MHRN suicide risk models and associated CDS. PCCs in HealthPartners clinics with CDS access will have access to the main OUD-CDS intervention for up to 30 months from date of implementation. PCCs in HealthPartners clinics randomized to the suicide model intervention will have access to the suicide supplement intervention for up to 12 months from date of implementation.

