### **J. Analysis**

#### **1. Study Hypotheses**

**H1:** Opioid Wizard-eligible patients (patients with OUD or at elevated risk of OUD/overdose) with elevated suicide risk in intervention clinics will have higher rates of completed CSSRS assessments than similar patients in control clinics.

**H2:** Opioid Wizard-eligible patients with elevated suicide risk in intervention clinics will have higher rates of engagement in their outpatient mental health care than similar patients in control clinics.

The hypotheses for this supplemental study predict that the Opioid Wizard + Suicide Risk Prediction intervention will increase (a) the likelihood that Opioid Wizard-eligible patients with elevated suicide risk are assessed at the index visit for immediate suicide risk using the CSSRS (H1); and (b) the rate of post-index primary care visits with a mental health diagnosis or with a behavioral health clinician (H2). These hypotheses will be tested using generalized linear mixed models so that each outcome may be estimated among intervention relative to control clinics while accounting for patient outcomes clustered within randomized clinics via a random clinic intercept. Both outcomes will likely be normalized with a Poisson-Normal link function, although the distribution of visits may warrant using a Negative Binomial-Normal link.

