## **3. Statistical Power**

Based on preliminary data, 1619 diagnosed (median=89, range=39-267 per clinic) and 3349 at-risk (median=41, range=19-129) patients were seen in the clinics eligible for the parent study over the course of one year for a total of 4968 (median=130, range=66-387) OUD-CDS-eligible patients. Assuming that 5%, 10% or 20% of approximately 2500 patients are evaluated and considered at high risk for suicide, we estimate that 125 (2500 \* 5%), 250 or 500 patients will be eligible for this study over one year of accrual.

A power analysis estimated the minimum detectable risk ratio for CSSRS and visit rates in intervention relative to control clinics. It relied on data-informed assumptions regarding the number of randomized clinics (n=15) and eligible patients per clinic (pts/clin =8, 16, 33); a range of clinic intraclass correlations consistent with those observed for other process measures at HealthPartners (ICCclin = 0.01, 0.03, 0.05); and outcome likelihood estimates in control clinics (screening=1%, 3%, 5%; visit rate=2, 3, 4/year).

Assuming 3% of control clinic patients are screened for suicide risk, the analysis will be powered (power=0.80,  $\alpha$ 2=0.05) to detect an outcome should at least 14.2% (ICCclin=0.01, 33 pts/clin, risk ratio = 4.72) to 65.0% (ICCclin=0.05, 8 pts/clin, RR=21.66) of intervention clinic patients be screened. The comparable range of detectable differences for outcomes with a 5% screening rate among control clinic patients is 16.8% (RR=3.36) to 54.8% (RR=5.80).

Power for Aim 2 analyses is not as sensitive to sample size assumptions. Under the most generous assumptions (ICCclin= 0.01, 33 pts/clin), small increases in visits rates (2.4 vs. 2.0, RR=1.22; 4.6 vs. 4.0, RR=1.15) will be detectable. Larger but still attainable increases (3.0 vs. 2.0, RR=1.49; 5.3 vs. 4.0, RR=1.33) will be detectable under the most conservative of assumptions (ICCclin=0.05, 8 pts/clin).

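### Section J.1 names no small-sample reference for the H2 test on 15 clinics, and section J.3's H2 detectable ratios fit a normal reference; on t with 13 df their power is about 73–76%, not 80%

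*Combined protocol and SAP*

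**What the plan says.** Section J.1 tests both hypotheses with generalized linear mixed models, "accounting for patient outcomes clustered within randomized clinics via a random clinic intercept". On the distribution it says: "Both outcomes will likely be normalized with a Poisson-Normal link function, although the distribution of visits may warrant using a Negative Binomial-Normal link". Neither J.1 nor any other section names a test statistic, a denominator-df method, a small-sample correction or a permutation test.

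The number of clusters is fixed by section E.2: "the clinics receiving access to the OUD-CDS (n=15) will be further randomized (1:1"). Section I describes this as simple randomisation giving an approximately even split.

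Section J.3 gives the H2 detectable ratios. For ICC 0.01 with 33 patients per clinic: "small increases in visits rates (2.4 vs. 2.0, RR=1.22; 4.6 vs. 4.0, RR=1.15) will be detectable". For ICC 0.05 with 8 per clinic: "Larger but still attainable increases (3.0 vs. 2.0, RR=1.49; 5.3 vs. 4.0, RR=1.33) will be detectable". The figures of 80% power and alpha 0.05 appear only in the preceding H1 sentence, and the reference distribution is not named. For H1 with a 5% control rate, J.3 reports "16.8% (RR=3.36) to 54.8% (RR=5.80").

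**The concern.** The H2 comparison is between clinics, so its error df is 15 − 2 = 13 however many patients accrue. A normal reference treats the between-clinic variance as known. With 13 df it is estimated imprecisely, and by maximum likelihood it is also biased downwards.

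Two things are at stake. First, if J.3 used normal quantiles, its H2 power and a valid 5% error rate do not hold together over much of its own range of ICC and clinic size. Second, Wald z, likelihood-ratio and Wald t tests of the same model give different error rates. With no reference named, that choice stays open until the data are in.

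**Working it through.** **Inputs (section J.3).** 15 clinics; m = 8 or 33 patients per clinic; N = 125 or 500 patients; ICC 0.01 or 0.05; control rate μ0 = 2 or 4 visits per year; power 0.80 and two-sided 0.05, taken from the H1 sentence. One year of exposure per patient is assumed at first.

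**Reproducing the plan's ratios.** With DE = 1 + (m − 1)·ICC, solve

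log RR = [2·q(0.975) + q(0.80)·√(2 + 2/RR)] · √(DE/(μ0·N)).

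Normal quantiles are 1.960 and 0.842; t quantiles on 13 df are 2.160 and 0.870. For the first row, DE = 1 + 32 × 0.01 = 1.32 and √(1.32/1000) = 0.0363. The normal version is (3.920 + 0.842 × 1.907) × 0.0363 = 0.201, so RR = 1.222.

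| μ0 | ICC, m | DE | N | Plan | Normal | t, 13 df |
|---|---|---|---|---|---|---|
| 2 | 0.01, 33 | 1.32 | 500 | 1.22 | 1.222 | 1.242 |
| 4 | 0.01, 33 | 1.32 | 500 | 1.15 | 1.153 | 1.167 |
| 2 | 0.05, 8 | 1.35 | 125 | 1.49 | 1.493 | 1.543 |
| 4 | 0.05, 8 | 1.35 | 125 | 1.33 | 1.330 | 1.362 |

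All four match the normal column and none matches the t column. The same formula with normal quantiles gives H1 ratios of 4.72, 21.8, 3.36 and 11.0, against the plan's 4.72, 21.66, 3.36 and 5.80. The last is an internal slip: 54.8% / 5% = 10.96.

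**Power at the plan's ratios, 7 against 8 clinics.** SE² = DE·[1/(7·m·μ0) + 1/(8·m·μ0·RR)]. First row: 1.32 × [1/462 + 1/644.2] = 0.00491, so SE = 0.0700 and log(1.22)/SE = 2.84. Normal power is Φ(2.84 − 1.96) = 81.0%; noncentral t on 13 df gives 74.7%. Across the four rows, normal power is 81.0, 79.6, 82.2 and 81.4%, and t power is 74.7, 73.1, 76.0 and 75.1%. Simulated power of the mixed-model statistic judged on t with 13 df is 73.7–76.5%.

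**Follow-up.** Section F.3 accrues patients over the first 9 of 12 months, giving 3–12 months each. If accrual were uniform, the mean would be (3 + 12)/2 = 7.5 months. Keeping DE fixed, the first row's 2.84 becomes 2.84 × √(7.5/12) = 2.24, and t power is about 55%. Over the four rows and two treatments of the clinic variance, the range is roughly 53–59%.

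**Null rejection if Wald z were used.** Simulation assumptions: Poisson random-intercept model fitted by maximum likelihood; 7 against 8 equal clinics; clinic log-variance ICC/((1 − ICC)·rate); 12 months per patient. There were 9,000 trials per cell at 3 visits per year (Monte Carlo SE 0.2–0.3 points) and 1,500 at 2 and 4 (SE about 0.5–0.8).

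| ICC, m | 2/year | 3/year | 4/year |
|---|---|---|---|
| 0.01, 8 | 4.4% | 4.9% | 5.1% |
| 0.01, 33 | 5.8% | 6.8% | 7.7% |
| 0.05, 8 | 6.9% | 6.7% | 6.9% |
| 0.05, 33 | 8.8% | 9.1% | 9.7% |

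With clinic sizes spread as in J.3 (range 66–387), the 3/year column becomes 5.3, 6.9, 7.5 and 9.2%. As a check, when clinic variance dominates, the limit for maximum likelihood is 2·P(T13 > 1.960·√(13/15)) = 9.1%. The same statistic on t with 13 df rejected 3.0–6.6% in the 9,000-trial cells.

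**The case against.** The strongest reply is that the plan never commits to Wald z. A t reference on between-clinic df is compatible with J.1 as written, so what is shown is an unspecified reference, not an invalid test. This stands. A reader might infer that the H2 test has a 9% error rate, but the documents do not support that. It needs Wald z, and also ICC 0.05 with 33 patients, a combination within J.3's grid for which no H2 ratio is quoted. At ICC 0.01 with 8 patients there is no inflation.

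Nor does J.3 state 80% power for H2. Its Aim 2 text says only that the ratios are detectable. Carrying 80% over is reasonable because J.3 describes one power analysis, but it is an inference. So is the normal reference. The match uses N = 125 with m = 8; with N = 15 × 8 = 120 the formula gives 1.506 and 1.338, which do not round to the plan's 1.49 and 1.33. The 7-against-8 formula with normal quantiles gives 1.217, 1.151, 1.474 and 1.324, close but not identical. Even so, no 15-clinic t variant tried reached 80% power at the stated ratios.

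The change in ratios is also modest (1.22 to 1.24, 1.49 to 1.54), and shorter follow-up costs more power than the switch from z to t. Both points stand, and the second shapes the fix. All simulations assume Poisson variation within clinics; the negative binomial form that J.1 allows was not simulated.

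**Conclusion.** The point holds in limited form. J.1 leaves the H2 reference unspecified with 13 between-clinic df, and J.3's H2 ratios fit a normal reference. On t with 13 df and 12 months per patient, power at those ratios is about 73–76%, and the 80%-power ratios are about 1.24, 1.17, 1.54 and 1.36. If Wald z were used, null rejection would be roughly 5–7% at the two scenarios quoted for H2 (6.7–6.8% in the larger run, with equal clinics) and about 9–10% at ICC 0.05 with 33 patients.

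A reader might extend this to H1. That is not supported: with few events, simulated Wald z null rejection for H1 was 0.0–6.2% in 11 of 12 cells and 8.9% in the other (5% rate, 33 patients, ICC 0.05). No general inflation is claimed there.

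The change should be made, but it is not a fatal defect. Confidence is medium, because both the normal reference and the 80% are inferred.

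**What to change.** 1. In J.1, state that the H2 p-value and 95% interval from the mixed model use a t reference on between-clinic df (13 for 15 clinics). Add one sensitivity analysis: either a permutation test over the realised allocation set (6,435 allocations for a 7:8 split) or a clinic-level t test. This also guards against the small excess, up to 6.6%, that the t reference can leave.
2. In J.3, name the reference and restate the H2 detectable ratios on it, allowing for unequal clinic sizes and F.3's 3–12 months of follow-up. The 12-month t ratios above show the size of the effect and should not be adopted as replacements.
3. In J.3, correct RR=5.80 to 10.96, or correct the 54.8% if that is the figure in error.

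The cost is a sentence of analysis wording, a recalculation and less favourable H2 figures. The planned model and trial conduct do not change.

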In both intervention and control clinics, suicide risk scores will be calculated for all Opioid Wizard-eligible patients (at high risk of OUD/overdose or diagnosed with OUD) and archive relevant EHR data to inform analyses. In intervention clinics, Opioid Wizard will alert PCCs to Opioid Wizard-eligible patients who are at increased risk of suicide and coach them through use of the Columbia Suicide Severity Risk Scale (CSSRS), a structured tool in the EHR that will help PCCs assess immediate suicide risk. Based on the resulting CSSRS score, Opioid Wizard will provide EHR links for risk-based referrals and follow-up recommendations, including care as usual, routine or

emergent referral to behavioral health, or transportation to the emergency department for further assessment.

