## **H. Data Collection and Management**

### **1. Measures of Primary and Secondary Outcomes**

Primary and secondary outcomes will be assessed using the data collected from the EHR via the OUD-CDS and from EHR (Clarity) data pulls.

Primary outcome measures include:

- a) Columbia Suicide Severity Rating Scale (CSSRS): frequency of completion, distribution of CSSRS scores, and Behavioral Health or ED referrals due to CSSRS scores
- b) Frequency and continuity of primary care and mental health visits (post-index visit)
- c) Identification of fatal and non-fatal suicide attempts, using ICD-10 codes
- d) Identification of Opioid overdose, using ICD-10 codes

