### **I. Randomization**

In the parent trial, HealthPartners primary care clinics (n=30) will be randomized to receive or not receive the intervention. In this supplemental study, simple randomization will allocate the intervention clinics (n=15) approximately evenly to receive or not receive access to the MHRN suicide risk models and associated CDS.

Each patient will be considered to belong to the clinic in which his or her first visit that is eligible for the OUD-CDS intervention (i.e., index visit) takes place, and as such will be in the treatment group to which their clinic was randomly assigned. Post-index visits may take place in the same or different clinics or treatment groups relative to the index visit and may or may not be eligible for the OUD-CDS to offer treatment recommendations. In keeping with an intent-to-treat principle, all index and post-index visits and outcome measures for each patient will be attributed to the treatment group assignment of the clinic where the index visit took place.

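### No baseline covariates are prespecified for the H2 visit-rate model, though useful ones exist or are probably obtainable; the unadjusted model is valid but gives up precision

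*Combined protocol and SAP*

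**What the plan says.** **Model.** Section J.1 (Study Hypotheses) is the only model specification for the two hypotheses. The H2 outcome is "the rate of post-index primary care visits with a mental health diagnosis or with a behavioral health clinician (H2". It is analysed by a generalized linear mixed model comparing arms, "accounting for patient outcomes clustered within randomized clinics via a random clinic intercept". Poisson is the expected distribution, but "the distribution of visits may warrant using a Negative Binomial-Normal link". No covariate or adjustment set is named there. Section J.4 adds only exploratory outcomes and subgroup comparisons.

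**Allocation.** Section I: "simple randomization will allocate the intervention clinics (n=15) approximately evenly". No stratification, matching or constraint is described.

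**Data.** Section D, for intervention and control clinics alike: "suicide risk scores will be calculated for all Opioid Wizard-eligible patients", with relevant EHR data archived for the analyses. Section F.3 makes OUD diagnosis, active medication for OUD, or model-based high risk part of eligibility, so OUD status is known at the index visit. Section H.1 takes outcomes from "data collected from the EHR via the OUD-CDS and from EHR (Clarity) data pulls". Its visit item covers the period after the index visit, and no pre-index count is listed.

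**The concern.** Patients differ in how often they use mental health care, and a patient's own past use is a natural candidate to predict later use. A model without baseline terms leaves that variation in the error. The number of clinics is fixed at 15, so adjustment is one of the few ways left to gain precision.

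The design does not compensate. With about 7 clinics against 8 and no balancing, the arms can differ by chance in baseline use, and the H2 estimate will carry that difference. If the plan says nothing, the team must either report an unadjusted result or choose covariates after outcomes are visible. The second course would be open to challenge.

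**Working it through.** **Inputs from the documents (sections J.3 and F.3).** Power 0.80; alpha 0.05, read as two-sided; 15 clinics, taken as 7.5 per arm; patients per clinic m = 8 to 33; ICC 0.01 to 0.05; control rate 2 to 4 visits a year; follow-up 3 to 12 months.

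**Assumed, because the documents give no value.** Negative binomial dispersion k; the share of k that covariates explain; mean follow-up of 7.5 months, which is (3 + 12)/2 under uniform accrual.

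**Step 1: reproduce the plan's H2 figures.** With n = 7.5m patients per arm, one year of exposure, control rate λ and DE = 1 + (m − 1) × ICC, solve

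log RR = (1.960 + 0.842) × √{DE × [1/(nλ) + 1/(nλRR)]}.

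| m, ICC | DE | λ | Computed RR | Stated RR |
|---|---|---|---|---|
| 33, 0.01 | 1.32 | 2 | 1.216 | 1.22 |
| 33, 0.01 | 1.32 | 4 | 1.150 | 1.15 |
| 8, 0.05 | 1.35 | 2 | 1.470 | 1.49 |
| 8, 0.05 | 1.35 | 4 | 1.321 | 1.33 |

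The agreement is close. The stated figures therefore appear to include neither overdispersion nor any covariate gain.

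**Step 2: gain under pure Poisson variance.** Here only the clinic component can be explained. The limit is DE = 1. At 2 visits a year the RR falls at best from 1.216 to 1.186 (33 patients, ICC 0.01) and from 1.470 to 1.398 (8 patients, ICC 0.05).

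**Step 3: gain if visits are overdispersed.** Replace each 1/(nλ) by (1/λ + k)/n, and 1/(nλRR) by (1/(λRR) + k)/n. Let covariates halve k. At λ = 2:

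| m, ICC | k | One year: unadjusted → adjusted | 7.5 months: unadjusted → adjusted |
|---|---|---|---|
| 33, 0.01 | 0.5 | 1.324 → 1.273 | 1.371 → 1.326 |
| 33, 0.01 | 1.0 | 1.413 → 1.324 | 1.454 → 1.371 |
| 8, 0.05 | 1.0 | 2.007 → 1.753 | 2.115 → 1.872 |

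If covariates explain only a quarter of k, the case with 33 patients, k = 1.0 and one year goes from 1.413 to 1.370.

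These figures let the covariates shrink the clinic component in the same proportion as the patient component. If only the within-clinic part shrinks, the same case (33 patients, k = 1.0, half explained, one year) goes from 1.413 to 1.347 instead of 1.324.

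**Step 4: the same gain as a variance ratio.** The per-patient ratio is (1/μ + k)/(1/μ + k(1 − R²)), where μ is expected visits per patient and R² is the share of k explained. For k = 0.5 to 1.0 and R² = 0.25 to 0.5:

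- One year: 1.14 to 1.50 (μ = 2) and 1.20 to 1.67 (μ = 4).
- 7.5 months: 1.11 to 1.38 (μ = 1.25) and 1.16 to 1.56 (μ = 2.5).
- k = 0: exactly 1.

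**Step 5: chance imbalance, 7 against 8 clinics.** Assume the baseline covariate has the outcome's ICC. The SD of the standardized arm difference is √[ICC + (1 − ICC)/m] × √(1/7 + 1/8).

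| m, ICC | SD | Chance of a difference above 0.25 SD |
|---|---|---|
| 8, 0.05 | 0.21 | 24% |
| 16, 0.03 | 0.16 | 11% |
| 33, 0.01 | 0.10 | 2% |

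**The case against.** The strongest reply is that this is a preference and not an error. A mixed model with a random clinic intercept, comparing randomized arms, is a valid primary analysis, and the intercept carries between-clinic variation into the standard error. That stands. A reader might infer that imbalance across 15 clinics biases or invalidates the H2 test. The documents do not support that; the cost is precision and the credibility of a single estimate.

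Four further limits stand:

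- Section J.1 is silent on covariates and does not rule them out. The parent protocol, to which section F refers, was not available.
- The pre-index visit count is an inference from the data source. The documented risk score may be the weaker predictor, because only patients at high suicide risk enter and its range is restricted.
- It is tempting to read the ratios in Step 4 as 14% to 67% more patients. They rest on assumed dispersion, assumed variance explained and a full year of exposure. They shrink to about 11% to 56% at 7.5 months and vanish at patient level under pure Poisson variance. Nor are they a true patient equivalent, since extra patients in 15 fixed clinics raise the design effect.
- The two harms do not peak together. Where the sample is largest (33 patients per clinic, ICC 0.01), an imbalance above 0.25 SD has only a 2% chance.

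A reader might also extend the point to H1. Control screening is assumed at 1% to 5%. With 125 patients, about 62 controls at 3% give roughly 2 expected events, too few to make another covariate a clear improvement.

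**Conclusion.** The point holds for H2 as a worthwhile improvement to a valid analysis. No adjustment set is prespecified, the allocation is not balanced, and two baseline values are known for every patient in both arms.

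The gain cannot be sized from the documents. It is small under the pure Poisson variance that the power section appears to use. It is larger under overdispersion, which section J.1 allows for: 1.41 to 1.32 in the illustrative case with 33 patients per clinic, and 1.45 to 1.37 at an assumed 7.5 months. The rise in the unadjusted detectable ratio from 1.22 to 1.41 comes from overdispersion and must not be counted as a cost of omitting covariates. The claim does not extend to the validity of the test or to H1.

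**What to change.** In section J.1, before outcome data are seen, specify for H2:

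- log person-time as an offset;
- fixed effects for log(1 + the 12-month pre-index count of the same visit type), the suicide risk score at the index visit, and OUD status (diagnosed or at-risk), stating how patients who qualify only through active medication for OUD are classed;
- the random clinic intercept as now, with the unadjusted model reported as a sensitivity analysis.

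Add the pre-index count to the data items in section H.1, after confirming that the Clarity pull can supply it. Leave the H1 model without covariates.

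The cost is a few sentences of plan text, an earlier start date for the visit query, and a history-length term for patients with under 12 months of prior records. If the count proves unobtainable, the other two covariates remain usable, probably with a smaller gain.
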